RRT Fidelity. We will be able to electronically track whether reports go out and whether they are timely/accurate. In addition, although we do not have a scalable way to track outreach attempts for 6,000 subscribers in Study 2, we will carefully document implementation processes and meet monthly with CareSource and intervention agencies, hear their experiences, offer feedback, and help problem-solve challenges. We will keep structured implementation process notes from these meetings for further analysis. Provider names will be included in the notes. All data from the implementation process feedback will be securely stored in REDCap. No names or identifiers will be used in any published works and will be accessible only to authorized research staff. Testing our service engagement mechanism will also help to elucidate steps in the causal chain (i.e., from the reports, to services provided, to suicide attempts).

Assignment to “intervention” and “control” conditions in the two studies is independent: participants may receive Intervention-Intervention, Intervention-Control, Control-Intervention, or Control-Control. Participants will be followed for 6 months following jail release using claims data.

C4. Data Analysis

Twelve months of historical (i.e., prior to arrest) and six months of prospective (i.e., after release) jail and Medicaid claims data will be extracted from CareSource’s Jail-Medicaid database for each participating subscriber for all measures, including demographics, diagnoses, suicide attempts, service use, number of arrests, dates of jail bookings/releases, and days incarcerated. Each eligible subscriber will be followed for 6 months following the index release from jail using claims data. CareSource will provide a limited dataset to the P50 Center (at MSU) that will be de-identified and analyzed by Center statisticians. Because these statisticians are employed by Brown University, an IAA will be established with both MSU and Brown University.

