For Aim 1, we will assess total number of subsequent attempts using the already-developed Mental Health Research Network (MHRN) algorithm for extracting MT suicide attempt information from claims data.^{10-12,48-58} The main effectiveness analysis is planned as a comprehensive model (i.e., including all 43,000 subscribers) evaluating Study 1 and Study 2 intervention effects, which provides optimal power and the ability to test interactive effects of interventions. All analyses will covary baseline (i.e., past year) values of dependent variables, and will use days incarcerated in the 6 months after the index jail release as an offset. **MT suicide attempts.** The main analysis framework will be logistic regression with the cumulative risk of a claims-data-identified suicide attempts requiring medical treatment over six months post-release as the outcome. We will secondarily use a negative binomial model and a count outcome for the number of MT suicide attempts. Our models will include robust standard errors due to clustering at the agency level. We will adjust for study month, and include indicator variables reflecting: (1) Study 1 intervention condition (i.e., CC or CAU); (2) inclusion in Study 2; (3) Study 2 intervention condition (i.e., RRT or Control). The ***hypothesis that the Study 1 intervention (CC) reduces suicide attempts*** is evaluated with magnitude and significance of parameter estimate associated with random assignment to the Study 1 intervention. The ***hypothesis that the Study 2 intervention (RRT) reduces suicide attempts*** is tested with the parameter estimate associated with exposure to the level 2 intervention. ***The hypothesis that the addition of flags and recommendations to provide SPI*** for individuals with past 12 months claims data identified suicide attempts (one component of the Study 2 intervention) ***will further reduce suicide attempts*** will be tested through the interaction between past history of suicide attempt and being in the Study 2 intervention condition. Identical analyses will be conducted for the other outcomes (all count outcomes): all cause injury and poisoning, outpatient BH visits, calls to CMS line, suicide-related ED visits/hospitalizations, and returns to jail detention. ***Exploratory.*** We will evaluate the interaction of Study 1 and Study 2 interventions by including an interaction term of the two indicators. ***Moderators.*** We will test sex, race/ethnicity, past suicide attempt (y/n), past 6-month BH visit (y/n), past 12-month arrest (y/n), area Deprivation Index,⁵⁹⁻⁶⁰ Mental Health Professional Shortage Area (HPSA)

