Using the IHI Framework for Going to Full Scale,⁶⁶⁻⁶⁷ this project will focus on sustainability and scalability. We will assess, maximize, and optimize intervention: (1) scalability (per the Intervention Scalability Assessment Tool⁶⁸); (2) sustainability (per the Program Sustainability Assessment Tool⁶⁹⁻⁷⁰) (3) feasibility, acceptability, and appropriateness to providers and systems (per the Acceptability of Intervention Measure,⁷¹ Intervention Appropriateness Measure,⁷¹ and Feasibility of Intervention Measure⁷¹); and (4) actual and recommended implementation strategies (via process mapping and implementation process/case notes).

Statistical power. Assumptions. We conducted a simulation study, allowing for variability in release dates, numbers eligible, and introducing a small intra-cluster correlation (ICC = .01). We assumed 43,000 eligible subscribers for Study 1, with 50% randomly assigned to CC. Based on last year's data, we assumed 6,000 eligible subscribers for Study 2. We expect that ~10% of the 6,000 ($n \sim 600$) will have past suicide attempt identifiable through CareSource claims data. We assumed a six-month risk of suicide attempt 0.05, but past 12-month claims data-identified suicide attempt increases this risk (i.e., .034 in absence of past-year suicide attempt, 0.204 with a past-year suicide attempt, odd ratio (OR) = 5), similar to SPIRIT. **Results.** We ran the simulation model 2001 times. Significance was assessed using a two-tailed type-I error level of 5%. Caring Contacts. We will have 85.6% power to detect an effect equivalent to an OR of 0.89. CC has been found to have much stronger effects than this in previous studies²² suggesting that we are adequately powered for CC. RRT. If we assume an intervention effect for Study 2 of 0.87 OR, we will have 88.3% power to detect this effect. For subscribers with a past year suicide attempt within Study 2 (who will be flagged to receive SPI), we will have 96.4% power to detect an OR of 0.63 (the OR detected for SPI in our previous trial, SPIRIT).⁴⁶ Having superadequate power for this test offsets concerns about providers potentially not providing SPI as instructed in this large, real-world study.

D. Material Inducements

Study 1

Provider focus groups: No material inducements will be provided for BH providers who engage in the focus groups. Providers will complete study-related procedures during work time and are typically not able to accept material inducements.

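### The Aim 1 suicide-attempt model leaves out pre-arrest covariates that the trial already extracts; prespecifying a short list would give a modest gain in power

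*Combined protocol and SAP*

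**What the plan says.** Section C4 takes twelve months of pre-arrest data for each subscriber, "including demographics, diagnoses, suicide attempts, service use, number of arrests", together with jail dates and days incarcerated.

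For the Aim 1 effectiveness model the same section says: "All analyses will covary baseline (i.e., past year) values of dependent variables". The other named terms are study month, indicators for Study 1 arm, inclusion in Study 2 and Study 2 condition, and an offset for days incarcerated after release. Standard errors are robust to clustering by agency; no agency fixed or random effect is named. The primary model is logistic, with a negative binomial count model as secondary.

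Sex, race/ethnicity, a past 6-month behavioral health (BH) visit and a past 12-month arrest appear in Aim 1 only as moderators. The Aim 3 cost model does list demographics and comorbidities as independent variables. Section D3 (Data Safety Monitoring Plan) says changes in outcomes, suicide attempts among them, will be shown with and without adjustment for participant characteristics, which it does not name.

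The power paragraph of C4 states: "We will have 85.6% power to detect an effect equivalent to an OR of 0.89"; "If we assume an intervention effect for Study 2 of 0.87 OR, we will have 88.3% power to detect this effect".

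**The concern.** Baseline variables that predict suicide attempts are in hand, date from before randomisation, and are used in the cost analysis, but not as covariates in the main effectiveness analysis. Two things are at stake.

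The first is power. Adjusting for prognostic baseline variables gives a more powerful test of a logistic treatment effect. For RRT, twelve agencies are randomised to four cohorts, three per cohort, and they provide mental health and/or substance use care. Chance differences in case mix between early and late cohorts feed into the RRT estimate, because nothing in the model absorbs them beyond the past-year outcome and study month.

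The second is prespecification. Section D3 commits to an adjusted result with an open covariate list, which leaves an avoidable choice to the analyst.

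**Working it through.** **1. Model terms against extracted data (suicide attempts)**

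| Extracted before arrest (C4) | Role in Aim 1 |
|---|---|
| Past-year suicide attempts | Covariate |
| Care at one of the 12 agencies in the prior 6 months | Covariate, through Study 2 inclusion |
| Demographics | Sex and race/ethnicity as moderators only |
| Diagnoses | None named |
| Other service use | Past 6-month BH visit as moderator only |
| Arrests | Past 12-month arrest as moderator only |

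**2. The plan's own power figures**

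Inputs from the power paragraph: two-sided 5%; 43,000 subscribers split 1:1 for CC; 6,000 for RRT; six-month risk 0.05. Formula: power = Φ(|p1 − p2|/SE − 1.960), with SE = √[(p1(1−p1) + p2(1−p2))/n per arm].

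- CC: odds 0.05/0.95 × 0.89 give p2 = 0.04475. Difference 0.00525; SE with 21,500 per arm 0.00205; z = 2.564; power 72.7%, against 85.6% stated.
- RRT, taken as 3,000 v 3,000 with no clustering: p2 = 0.04378; difference 0.00622; SE 0.00546; z = 1.139; power 20.6%, against 88.3% stated.

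Neither figure reproduces. The simulation code and full settings are not in the documents, so the cause cannot be identified.

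**3. CC with past-year attempt in the model**

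Risks are 0.034 without and 0.204 with a past-year attempt. The 10% prevalence is stated for Study 2; applying it to all 43,000 is an assumption. Information per stratum is ab/(a+b), with a = n·p(1−p) in control and b likewise under CC.

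- No past attempt (19,350 per arm): 0.034 becomes 0.0304; a = 635.5, b = 569.9; information 300.5.
- Past attempt (2,150 per arm): 0.204 becomes 0.1857; a = 349.1, b = 325.2; information 168.4.
- SE = 1/√468.8 = 0.0462; z = 0.1165/0.0462 = 2.523; power 71.3%.

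**4. CC with further covariates**

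The documents give no prognostic strength for the other variables. They are represented by a normal prognostic score added within each past-attempt stratum, holding the stratum risks and the past-year-adjusted OR fixed. Gain in effective sample = (z adjusted / z base)² − 1.

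| Model AUC (assumed) | Conditional OR | SE of log-OR | z | Power | Gain |
|---|---|---|---|---|---|
| 0.66 (past attempt only) | 0.890 | 0.0462 | 2.523 | 71.3% | – |
| 0.74 | 0.888 | 0.0466 | 2.547 | 72.2% | 1.9% |
| 0.78 | 0.885 | 0.0472 | 2.579 | 73.2% | 4.4% |
| 0.81 | 0.882 | 0.0480 | 2.622 | 74.6% | 8.0% |
| 0.84 | 0.877 | 0.0491 | 2.678 | 76.4% | 12.7% |

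The SE rises in every row. Power improves because the conditional OR moves further from 1. A separate calculation with assumed ORs of 1.5-3 for serious mental illness (SMI) and substance use disorder (SUD) gave a gain of about 1-5%, or 0.3-2 power points. The working range is therefore 1-8%, with the 0.84 row as an optimistic outer case. Starting instead from the stated 85.6% (z = 3.022), an 8% gain gives z = 3.022 × √1.08 = 3.141 and power 88.1%.

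**5. RRT**

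Setting: stepped-wedge schedule (start months 4, 6, 8, 10), 12 agencies, ICC 0.01, agency-robust variance, linear-probability approximation, and the other 37,000 subscribers sharing the month effects.

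- Power is 12.7% with past-year attempt in the model. It is 13.1% if individual-level R² rises from 0.054 to 0.12, and 15.2-15.8% if covariates also explained half of the between-agency variance.
- Simulation of the C4 terms (offset and CC arm omitted; 12 × 500 plus 37,000 subscribers; OR 0.87): without SMI and SUD covariates the RRT variance was 5-13% larger when agencies differ widely (SMI 10-70%, SUD 20-90%; ORs 1.5-2; 2,000 trials each). It was 1-2% larger when they differ little (SMI 25-55%, SUD 40-70%; ORs 1.5-3; 1,000 trials each). The spreads are assumptions; the Background gives only overall shares of 16% SMI and 50% SUD.

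**6. Comparison with the power gap**

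Moving CC from 71.3% to 85.6% needs (3.022/2.523)² = 1.43, or about 43% more effective sample. The working range is 1-8%.

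**The case against.** **The plan adjusts for more than the baseline outcome.** This stands. Study month and Study 2 inclusion are in the model, and the latter marks recent agency care. A reader might infer that the past-year outcome is the sole adjustment; C4 does not support that. For BH visits and returns to jail, the baseline value is itself service or jail history, so the gap mainly concerns suicide attempts.

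**The quoted sentence may be broader than it looks.** Its plural could put the past-year values of all outcomes into every model, covering or nearly covering BH visits, ED/hospital use and arrests. The ambiguity is real. On either reading, diagnoses and demographics stay out of the prognostic set.

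**Section D3 already promises adjustment.** True, but without naming variables or linking them to the Aim 1 model. That is a reason to fix the list.

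**The gain may be negligible.** The plan's dominant predictor is already included. A simulation of 150 trials with modest assumed effects (ORs 1.5 for SMI, 1.5 for SUD, 1.2 for sex, 1.15 per arrest) gave a ratio of 1.00 (95% interval 0.99-1.01); stronger effects (2.5, 2.5, 1.5, 1.4) gave 1.03 (1.01-1.05). This stands as a caution: with weak predictors the gain could be close to nothing.

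**CC is individually randomised 1:1 with about 21,500 per arm.** Also true. A reader might infer that the unadjusted CC estimate is biased; the design gives no ground for that.

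**Conclusion.** The point holds as a minor, low-cost improvement. The Aim 1 model for suicide attempts omits prognostic covariates that the trial already extracts, and section D3 leaves its adjustment set open.

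For CC the expected benefit is roughly 1-8% in effective sample, up to about 3 power points, under assumed predictor strengths. For RRT the benefit depends on how far agencies differ in case mix: variance without the covariates is about 1-2% larger if they differ little, up to about 13% if widely. RRT power stays low either way on the stated inputs.

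Three stronger readings are not supported. Adjustment is not free precision for a logistic OR, since the SE rises while the conditional OR moves from 1. The percentage should not be turned into a count of extra subscribers, because it rests on predictor strengths that the documents do not give. And adjustment does not rescue the stated power: for CC the gap corresponds to about 43% more effective sample.

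**What to change.** In C4, prespecify these pre-arrest covariates for the primary logistic and secondary negative binomial models: age, sex, race/ethnicity, SMI diagnosis, SUD diagnosis, past-year outpatient BH visits, past-year ED/hospital use and past-year arrests. State their coding. Say whether the baseline-values sentence means each outcome's own past-year value or all of them. State that this list is the set of participant characteristics meant in section D3. Show the model without the list as a sensitivity analysis.

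The cost is SAP wording and no new data. At 5% of 43,000, about 2,150 expected events carry a list of this length without overfitting concern for CC. Section D3 has the DSMB approve the analysis plan, so the change should go to the DSMB and be fixed before outcomes by arm are seen. The downside is that the reported OR becomes conditional on these covariates and should be labelled so.

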
score,⁶¹⁻⁶² and per capita incarceration (by zip code) as moderators of intervention effects on suicide attempts, using $p < .01$.

Aim 2 will be analyzed by examining the number of outpatient BH claims in the 6 months following the index jail release and number of calls to the CMS line as mediators of the intervention/s effects on suicide attempts by adding this variable to our effectiveness model. Mediation is revealed by the extent to which the intervention effect parameter estimates change with the addition of the putative mediator. We will use bootstrap methods to estimate 95% uncertainty intervals around the mediated effect.

For Aim 3, our grants accounting will capture the costs of the CC mailings. Treatment received as part of the intervention and CAU conditions (including outpatient, inpatient, and ED mental health and suicide-related medical care visits) will be tracked using claims data. Costs of CAU will be computed as CareSource payments plus co-pay and deductibles. We will add training costs for providers but exclude other research costs that would not be incurred if RRT was standard care. The primary cost-effectiveness (CE) measure, computed from a societal perspective for each intervention arm, will be the program cost divided by the sum of suicide attempts prevented. We also will assess the net cost of the program from a MCO perspective. That measure will exclude patient payments from costs.

Costs (and savings) in future years will be discounted to present value in the year of jail release using the 3% discount rate recommended by the Second Panel on Cost-Effectiveness in Health and Medicine.⁶³ We will bootstrap the 95% uncertainty interval around the CE ratio. Analyses from the MCO perspective will compute the change in claims costs by running a generalized linear model (GLM) with gamma, inverse Gaussian, or Poisson variance based on data distribution, the log link function, and robust standard errors.⁶⁴ We will use a 2-part GLM unless less than 5% of patients have zero costs. Independent variables will include treatments received, demographics, Elixhauser co-morbidities,⁶⁵ and days of MCO coverage after jail discharge. We also will track the MCO separation rate post-discharge by group.

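### Days in jail after release is used as the model offset: it runs against time at risk, has no usable value for people not re-jailed, and can itself be changed by the intervention

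*Combined protocol and SAP*

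**What the plan says.** Section C4 (Data Analysis, Aim 1) sets one rule for all its models: they "will use days incarcerated in the 6 months after the index jail release as an offset". No log, no complement (days at liberty) and no handling of zero days is stated there or elsewhere.

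The rule reaches these analyses:

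- **Primary model:** "logistic regression with the cumulative risk of a claims-data-identified suicide attempts requiring medical treatment over six months post-release as the outcome". It carries both the Caring Contacts (CC) and the RRT hypothesis tests and is "planned as a comprehensive model (i.e., including all 43,000 subscribers".
- **Secondary model:** a negative binomial model for the number of attempts.
- **Other outcomes:** identical analyses are promised for a list that ends "calls to CMS line, suicide-related ED visits/hospitalizations, and returns to jail detention".
- **Aim 2:** two putative "mediators of the intervention/s effects on suicide attempts by adding this variable to our effectiveness model", so the offset carries over.

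The Aim 3 cost model lists no offset. It does list "days of MCO coverage after jail discharge" as a covariate, and the plan adds: "We also will track the MCO separation rate post-discharge by group". The power simulation is described as "allowing for variability in release dates, numbers eligible, and introducing a small intra-cluster correlation (ICC = .01"; its listed assumptions include neither jail days nor a re-jailing rate.

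**The concern.** An offset normally stands for the logarithm of exposure, so that expected events scale with time at risk. Here the variable named is the time a subscriber spends back in jail. Four difficulties follow.

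1. It moves the wrong way relative to community time.
2. It is zero for everyone not re-jailed. Section C2 (CC letters) treats re-arrest as something that happens to some subscribers only.
3. It accrues after randomisation, which section C2 places at index release, and return to jail is something the interventions may change.
4. When return to jail is the outcome, the offset is produced by that outcome.

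The primary model cannot be fitted sensibly to the full sample as written. An analyst would have to choose a workaround, possibly after seeing data, and the estimated effect depends on which one is chosen.

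**Working it through.** **Benchmark.** The plan states 85.6% power for CC at an odds ratio of 0.89, with 43,000 subscribers split 1:1, risk 0.05 and two-sided 5%. In closed form:

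- CC odds = (0.05/0.95) × 0.89 = 0.0468, so CC risk = 0.0447.
- Information = 1/(1/1021 + 1/919) = 484, so SE = 0.0455.
- Power = Φ(0.1165/0.0455 − 1.96) = 73%.

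The stated figure is not reproduced, and the plan does not say whether its simulation used an offset. Nothing below depends on it. Comparisons are with the no-offset model fitted to the same simulated data.

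**Direction.** Taking six months as 182 days, 0, 36 and 100 jail days leave 182, 146 and 82 community days. A coefficient fixed at +1 makes predicted risk rise along that sequence.

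**Log(days).** log(0) is minus infinity. Trial fits of both the logistic and the negative binomial model failed outright. Dropping zero-day subscribers keeps about 20–40% of the sample if 20–40% are re-jailed.

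**Raw days.** The odds are multiplied by e = 2.72 per day: e^10 ≈ 22,000 and e^36 ≈ 4.3 × 10^15. One logistic fit returned a CC coefficient of −3.17 against a true −0.117.

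**Log(days+1), by hand.** In a Poisson model with arm only, the estimate is the ratio of events divided by the ratio of mean (days+1). Let m be mean jail days per control subscriber, and let CC cut re-jailing by 10%.

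- No true effect on attempts: (1+m)/(1+0.9m). This is 8/7.3 = 1.10 at m = 7 and 30/27.1 = 1.11 at m = 29, which is roughly the span of m under the assumptions below. (The small fall in attempts from more or less time at liberty is ignored.)
- Returns to jail, true rate ratio 0.90: 0.90 × 1.096 = 0.99 at m = 7 and 0.90 × 1.107 = 1.00 at m = 29. The offset cancels the effect being tested.

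**Log(days+1), logistic simulation.** There were 200 trials per cell with N = 43,000 at 1:1. Ten per cent had a past attempt, and risks were 0.034 and 0.204 (Statistical power paragraph), acting on days at liberty. The model contained CC and past attempt, with robust SE.

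Assumed, because the documents give no figure: 20% or 40% re-jailed, and a CC effect on re-jailing of none, 5% or 10%. Median stay was 14 or 36 days; section 2.B gives 36. Stays were log-normal (sigma 1.3), with total days capped at 175. Ranges run over the four share-by-stay settings.

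| True OR | CC effect on re-jailing | No offset | log(days+1) |
|---|---|---|---|
| 0.89 | none | power 65–74% | OR 0.85–0.87, SE 40–65% larger, power 53–64% |
| 0.89 | 5% cut | power 58–68% | OR 0.91–0.94, power 13–26% |
| 0.89 | 10% cut | OR 0.89–0.91, power 50–68% | OR 0.96–1.02, power 3–8% |
| 1.00 | none | – | OR 0.99–1.01, 3.5–5% rejections |
| 1.00 | 10% cut | OR 1.00–1.01 (separate run, 40 trials per cell) | OR 1.12–1.18, significant harm in 37–63% |

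Monte Carlo error is about 3.5 points on power and 0.005 on the log(days+1) odds ratios. Log(days) among the re-jailed only gave OR 0.87–0.90 but 9–30% power: lost sample, little shift.

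A separate simulation with different assumptions (35% re-jailed, median 12 days, 3-point reduction, 40 runs) gave OR 1.11 with 40% rejection when there was no true effect, and 0.985 with 10% rejection when the true OR was 0.89.

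**Returns to jail, simulated** (robust Poisson, true rate ratio 0.90). No offset gave 0.90, detected in 99–100% of trials. Log(days+1) gave 0.99–1.00, detected in 4–10%. Log(days) gave 1.00, detected in 2–6%.

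**The case against.** The strongest reply is that the sentence is a loosely worded exposure adjustment and days not incarcerated were meant. On that reading the harm nearly disappears for attempts: with a true OR of 0.89 and a 10% cut in re-jailing, log(days at liberty) gave 0.890–0.895. This may well be the intention, and the repair would then be close to a wording correction. It does not rescue the text, which names the opposite quantity. It also leaves the returns-to-jail model with an offset determined by its outcome, and log time is not a natural offset in a logit model for cumulative risk.

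Other points stand in part:

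- **Person-time is always measured after randomisation.** True, and not an error in itself. It matters here because return to jail is a study outcome that the interventions may change.
- **Attempts made in custody may count.** Time at risk would then be a constant six months, and the offset would be unjustified rather than reversed.
- **The large distortions are conditional.** They need both log(days+1) and a CC effect on re-jailing, and the documents give neither. Without that effect there is no excess of false positives, only lost precision and some distortion of a true effect.
- **The simulation is simpler than the planned model.** It has no clustering, study month or Study 2 terms, so nothing is quantified for RRT. For returns to jail, a small check with negative binomial models gave rate ratios of 0.95–0.99 rather than 0.99–1.00: still attenuated, but somewhat less.
- **Count or rate is a choice of estimand.** Fair. The investigators should choose and state it.

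**Conclusion.** The concern holds. As written, the offset is wrong, not merely under-described: log(days) cannot be computed for much of the sample, raw days give meaningless odds, and log(days+1) mixes effects on re-jailing into effects on attempts. The returns-to-jail analysis is circular under any jail-day offset. These conclusions follow from the text and need no assumed rates.

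The size does depend on assumptions. With 20–40% re-jailed and log(days+1), the cost ranges from standard errors 40–65% larger, when CC leaves re-jailing unchanged, to the near-total loss of a true OR of 0.89 or a false harmful OR of 1.12–1.18, when CC cuts re-jailing by 10%. The effect on the RRT test was not quantified. Because the sentence governs both primary hypothesis tests and Aim 2, it should be corrected before any outcome data are analysed.

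**What to change.** Replace the offset sentence in section C4 with the following specification.

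- **Primary six-month logistic model:** no offset, giving the as-randomised contrast.
- **Count models:** an as-randomised analysis with no jail-based offset. Add a rate analysis with offset log(days not incarcerated, and enrolled where available) as a sensitivity analysis, and acknowledge that this exposure is also post-randomisation. If the investigators want the rate as their main count estimand, they should say so in advance.
- **Zero rule for the rate analysis:** for example, subscribers with no days at liberty are counted by arm and left out of that analysis only.
- **Returns to jail:** no jail-day offset in any version.
- **Aim 2:** carry over the same specification. Aim 3 needs no change.

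The cost is one sentence of the plan and a small sensitivity analysis. Booking and release dates are already in the planned extract, and coverage days are already needed for the Aim 3 cost model.
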